- Interpretation: These experiments will lead to multiple insights. Through segmental interactions, confirmation of Hypothesis 1.2 would further demonstrate the ability of CES to positively modulate motor neuron excitability, and confirmation of hypothesis 1.3 would indicate the potential for CES to reduce spasticity⁴⁵. Confirmation of speculative hypothesis 1.2 would demonstrate that at high intensity, CES pulses travel via efferent nerve roots and collide with retrogradely traveling F-waves.

Aim 1 data analysis: Peak-to-peak amplitude of all conditioned pulses will be normalized to the amplitude of unconditioned pulses. For each interaction paradigm, analysis of variance (ANOVA) with factors of subject group, stimulus intensity, interstimulus interval, and muscle will be performed. Post hoc pairwise comparisons will be made using Tukey’s method. *Power:* Using a conservative predicted effect size of 0.4 for each interaction paradigm, >80% power will be achieved with a sample size of 10 for each analysis (repeated measure ANOVA) with four factors. 15 subjects in each group (SCI, able-bodied) will undergo testing.

Aim 1 Timeline (Table 2):

Each subject will undergo three testing sessions on separate days, with a minimum of 24 hours and a maximum of two weeks between visits. Per subject, Aim 1 participation would therefore take 3 to 28 days. 30 subjects will be enrolled, resulting in 90 total testing sessions. A conservative projection of completing two testing sessions per week would result in a timeline of 45 weeks or 11-12 months for completing Aim 1.

Aim 2: Determine optimal CES parameters for acutely facilitating concurrent wrist and hand movements.

Volitional limb movements depend on the same corticospinal and spinal motor circuits as those activated by TMS and F-waves. Therefore, since preliminary data shows that subthreshold CES facilitates TMS responses, CES may also be able to facilitate volitional limb movements. The experiments in Aim 2 will shed light on this clinically applicable question.

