Volitional motor tasks: Maximal voluntary contraction (MVC) will be defined as the largest response from 3 attempts at maximal effort prior to testing. Effort will be measured using a customized dynamometer or the root mean square (RMS) of electromyographic activity in the target muscles. The tasks are: opposition between the tips of the thumb and third finger (C8-T1 levels), or wrist extension laterally against a mounted load cell (C6 level). A combined finger opposition/wrist extension task will also be tested. Subjects will be instructed to perform tasks at target effort levels based on real-time display of ongoing EMG or force output.

CES-motor task interaction: Subjects will be given a synchronized audio and visual cue to perform volitional motor tasks at 100%, 50%, or 10-20% of MVC. Volitional tasks will be performed for a maximum of 4 continuous seconds. At least 10 seconds will elapse between each CES/motor task combination. Conditioning CES pulses (or sham pulses at 0% intensity) will be delivered at intensity ranging between 30%-175% of CES resting motor threshold. For subthreshold conditioning CES, either single or “theta bursts” (3 pulses at 50 Hz)¹⁹ will be delivered. Motor task, effort level, and CES parameters will be varied in pseudorandom order, until 8-10 responses per parameter have been recorded.

Aim 2 Outcomes:

- Facilitation: At each muscle, the effect of CES pulses on RMS electromyographic activity over the subsequent 200 ms (in 25 ms bins) will be measured and normalized to the baseline RMS from the preceding 100 ms.
- Silent period: At each muscle, the duration of electromyographic silence is measured from the end of the CES-evoked potential until the resumption of volitional muscle activity (defined as mean rectified EMG amplitude less than or greater than mean baseline activity + 2 standard deviations⁶⁸, respectively).

Hypothesis 2.1: Subthreshold CES will *facilitate* concurrent wrist and hand muscle activation.

Hypothesis 2.2: High-intensity CES will transiently *inhibit* concurrent wrist and hand muscle activation.

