Interpretation: Confirmation of Hypothesis 2.1 would substantiate the predicted findings of Hypotheses 1.1 and 1.2 and our early preliminary data that indicate CES’s ability to positively modulate corticospinal and/or motor neuron excitability. We expect optimal facilitation when subthreshold CES is delivered at closer to motor threshold intensity. We do not know whether the effects will differ depending on intensity of volitional effort, but if so, further experiments could investigate the roles played by peripheral, spinal, and supraspinal components of effort intensity⁶⁹. Furthermore, these experiments would shed light on whether CES modulates ongoing motor neuron activity differently at different spinal levels during level-specific motor tasks (thumb-finger opposition C8-T1, wrist extension C6). Most importantly, confirmation of Hypothesis 2.1 would represent an opportunity to directly translate and test this paradigm for clinical benefit by combining repetitive subthreshold CES with repetitive task-oriented physical exercise training.

If high-intensity CES inhibits concurrent volitional activity as predicted by Hypothesis 2.2, this would be analogous to the ‘cortical silent period’ (CSP) noted when cortical TMS is delivered during volitional contraction^{5,6}. The early phase of CSP (the first 50-75 ms after onset of the cortical motor-evoked potential) is mediated by poorly understood spinal mechanisms⁵. Our observations of the onset and duration of a ‘spinal silent period’ (SSP) in response to CES would shed mechanistic light on this phenomenon.

Aim 2 Data analysis: Rather than peak-to-peak amplitude, the effects of CES on concurrent volitional muscle contraction will be measured using RMS as described above. Repeated-measure ANOVA with factors of subject group, volitional effort intensity, CES intensity, post-stimulus timebin, and muscle will be performed. Post hoc pairwise comparisons will be made using Tukey’s method. Although we can only speculate on the predicted effect size, with use of a conservative effect size of 0.4 for each interaction paradigm, >80% power will be achieved with a sample size of 10 for each analysis (repeated measure ANOVA with five factors). 15 subjects in each group (SCI, able-bodied) will undergo testing.

Aim 2 Timeline:

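### The Aim 2 ANOVA has no term for motor task, and pulse pattern, if it is varied, is missing from the models of both Aims

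*Combined protocol and SAP*

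**What the plan says.** All references are to Section 3 of the combined protocol and SAP.

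**Tasks.** Volitional motor tasks (Aim 2) ties opposition of thumb and third finger to C8-T1 and wrist extension to C6, then adds a third task: "A combined finger opposition/wrist extension task will also be tested". CES-motor task interaction states: "Motor task, effort level, and CES parameters will be varied in pseudorandom order", with 8-10 responses collected per parameter.

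**Models.** Aim 2 Data analysis: "Repeated-measure ANOVA with factors of subject group, volitional effort intensity, CES intensity, post-stimulus timebin, and muscle will be performed". The power sentence that follows counts five factors, which matches the list. Aim 1 data analysis lists subject group, stimulus intensity, interstimulus interval (ISI) and muscle, and its power sentence counts four.

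**Pulse pattern.** CES-motor task interaction says: "For subthreshold conditioning CES, either single or" three-pulse bursts at 50 Hz. The methods for the CES-TMS and CES-peripheral nerve experiments of Aim 1 contain a similar sentence.

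**What the results are for.** The Aim 2 title is: "Determine optimal CES parameters for acutely facilitating concurrent wrist and hand movements". The Aim 2 Interpretation says the experiments would help show "whether CES modulates ongoing motor neuron activity differently at different spinal levels during level-specific motor tasks". This is an interpretive statement, not a numbered hypothesis. The CES-TMS Interpretation takes facilitation at ISI 2-20 ms as support for segmental summation, and at 20-60 ms as support for sensory cortical facilitation.

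**The concern.** Two experimental variables have no place in the stated models. Motor task is certainly varied. Pulse pattern probably is.

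The level-by-task question needs a contrast that involves task, muscle and CES together. A model without task can compare muscles only after averaging over tasks. A facilitation that appears only while a muscle is engaged is clinically different from a weaker one that is always present, because the protocol proposes to combine CES with task-oriented training. The stated model would not tell the two apart.

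Pulse pattern is one of the CES parameters that Aim 2 might optimise, and without a term it cannot be compared. In CES-TMS the pattern also bears on mechanism, because a burst occupies more time than the early window allows.

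If the plan does not fix these terms in advance, any split by task or pattern will be chosen after the data are seen.

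**Working it through.** **1. The plan's own figure.** For Aim 2 the plan claims more than 80% power with 10 subjects, "with use of a conservative effect size of 0.4 for each interaction paradigm". It gives no effect-size metric, alpha, within-subject correlation or number of levels. Taking Cohen's f = 0.4, alpha 0.05, correlation 0.5 and one group of 10, noncentral-F power for a within-subject effect is 0.806 with 4 repeated measurements and 0.867 with 5. With correlation from 0 to 0.7 and 2 to 8 measurements, it runs from 0.35 to above 0.99. The claim can be met, but it does not bear on which factors are in the model.

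**2. Varied or recorded, against modelled (Aim 2).**

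| Factor | In the design | In the ANOVA |
|---|---|---|
| Subject group | yes | yes |
| Volitional effort | yes | yes |
| CES intensity | yes | yes |
| Post-stimulus time bin | yes | yes |
| Muscle | yes | yes |
| Motor task (3) | yes | no |
| Pulse pattern (subthreshold CES only) | single or burst; whether both is unclear | no |

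Muscle does not stand in for task, because the plan does not tie each muscle to one task.

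**3. What averaging over task does.** Assume that CES acts only on the engaged muscle, with effect a in the thumb muscle and b in the wrist extensor, and that the three tasks are equally frequent.

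| Task | Thumb muscle | Wrist extensor |
|---|---|---|
| Opposition | a | 0 |
| Wrist extension | 0 | b |
| Combined | a | b |
| Mean over tasks | 2a/3 | 2b/3 |

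The contrast between muscles in the averaged model is 2a/3 - 2b/3 = 2(a - b)/3. The level difference keeps its sign and loses one third of its size.

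Dependence on task disappears altogether. For illustration, let a = b = 20%. The averaged model shows 2 x 20/3 = 13.3% in each muscle and a muscle difference of 0. The per-task muscle differences are +20, -20 and 0 points. A CES effect of 13.3% in both muscles under every task would give the same averaged result.

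**4. Burst length against the CES-TMS windows.** At 50 Hz the pulses are 1000/50 = 20 ms apart, so three pulses span 2 x 20 = 40 ms. The early window is 20 - 2 = 18 ms wide and the late window 60 - 20 = 40 ms wide. No burst fits the early window. A burst fits the late window only with pulses at 60, 40 and 20 ms before the test pulse.

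The table gives pulse times in ms before the test pulse; negative values fall after it.

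| Pulse that sets the ISI | ISI label 10 ms | ISI label 30 ms |
|---|---|---|
| Last | 50, 30, 10 | 70, 50, 30 |
| Middle | 30, 10, -10 | 50, 30, 10 |
| First | 10, -10, -30 | 30, 10, -10 |

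For every label from 2 to just under 20 ms, at least one pulse falls in the late window or after the test pulse, whichever pulse is the reference. For labels above 20 ms, the last-pulse reference puts no pulse in the early window, while the other two can. The Timing subsection aligns pulses by arrival at the motor neurons. A fixed conduction delay shifts all three pulses equally, so the 40 ms span is unchanged.

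**The case against.** The strongest reply is that no numbered hypothesis is harmed. That stands. Hypotheses 2.1 and 2.2 can each be tested against baseline or sham. In the illustration above, facilitation still shows as 13.3% in each muscle. With f = 0.4, alpha 0.05, correlation 0.5, 5 measurements and 30 subjects, an effect present in two of three tasks averages to f = 0.267 with power 0.97. The reassurance has a limit: an effect in one of three tasks averages to f = 0.133 with power 0.41.

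A second reply is that the plan may intend several models. Aim 1 runs an ANOVA for each interaction paradigm, and the Aim 2 power sentence uses the same phrase. Separate models by task are therefore possible. But Aim 2 has a single interaction heading, and no text describes such a split.

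A reader might infer that the model can say nothing about spinal levels. Step 3 shows otherwise: the contrast shrinks but survives. In the illustration with a = b, a zero difference between levels is even correct. What is hidden is the dependence on task.

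A reader might also take it as settled that patterns are mixed within a paradigm, or that bursts and single pulses are known to act in opposite directions. The documents support neither. The phrase offering one pattern or the other could mean one pattern throughout, although pseudorandom variation of CES parameters suggests otherwise. The background statement on bursts that inhibit or excite concerns TMS. The one on spinal pulses 20-50 ms apart concerns low suprathreshold intensities, whereas bursts here are subthreshold.

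Finally, a reader might infer that CES-TMS cannot separate the two mechanisms at all. That is too strong. Single-pulse trials, if collected, keep the reading available, and with the last pulse as reference the late window stays free of early pulses. Nor can a share of affected trials be given, because the plan has no ISI grid.

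**Conclusion.** The point holds, in two parts of unequal strength.

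The task omission is firm on the text. The stated Aim 2 model averages over a factor that the design varies and that the level-by-task question needs. It cannot show whether the CES effect in a given muscle depends on the task. It also dilutes differences between levels, by one third if CES acts only on engaged muscles and the tasks are equally frequent.

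The pattern omission is conditional. If both patterns are used within a paradigm, neither Aim's model can compare them. If one pattern is used throughout, this comparison falls away and the task point is untouched.

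The burst arithmetic does not depend on that condition: CES-TMS burst trials labelled 2-20 ms do not isolate the early mechanism. Whether the 20-60 ms window is affected depends on which pulse sets the ISI.

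The plan should be changed, because the change is specific and cheap. The effect is on the interpretation of results, not on the validity of the numbered hypotheses.

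**What to change.** **Aim 2.** Add motor task to the model, with task x muscle x CES intensity. Fit a mixed model that uses the cells actually collected, since 8-10 responses are gathered per parameter and not clearly per cell. Report the CES contrast within each task, by muscle, with confidence intervals.

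**Both Aims, where both patterns are used.** Add pulse pattern, nested within subthreshold CES where bursts are limited to it, or analyse bursts separately. Base the 2-20 versus 20-60 ms reading, and any comparison of subthreshold with suprathreshold CES, on single-pulse trials. The latter would otherwise mix intensity with pattern.

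**Clarifications only.** State whether one or both patterns are used. Name the pulse that sets the burst ISI. For Aim 2 bursts, say that the baseline ends before the first pulse and where the 25 ms bins begin.

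**Cost.** This is a change of analysis wording for conditions already in the design, and no extra trials are requested. The downside is a longer model and three-way estimates that may be imprecise; their power cannot be derived from the documents, hence the confidence intervals.

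Full crossing is not proposed. Assume sham, one suprathreshold intensity, and k subthreshold intensities each given as single pulse and burst. The trial count is then 3 tasks x 3 efforts x (2k + 2) x 8, which is 288 for k = 1 and 576 for k = 3. The plan also requires: "At least 10 seconds will elapse between each CES/motor task combination". At 10 s per trial this is 288 x 10/60 = 48 minutes and 576 x 10/60 = 96 minutes, and 10 s is a minimum gap.
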